3.4 Removal of Subjects from the Study

A subject will not participate further in the study under the following conditions:

1. Withdrawal by Subject: subjects have the right to withdraw from the study at any time. However, if a subject withdraws consent because of experiencing an adverse event, the reason for subject termination should be documented as the adverse event.
2. Adverse Event: a clinical or biological adverse event or intercurrent condition(s), requiring study drug discontinuation, whether or not related to the study drug

If grade 3 findings (defined as severe or medically significant but not immediately life-threatening; hospitalization or prolongation of hospitalization indicated; disabling; limiting self-care activities of daily living [ADL] such as bathing, dressing, undressing, feeding self, using the toilet, taking medication, but not bedridden), according to the CTCAE²⁹, are noted in a subject, he/she must be promptly evaluated by the Investigator (including repeat tests, evaluation of the baseline parameters, concomitant medications, etc.) for potential withdrawal from the study. Every effort should be made to discuss with the study's Medical Monitor prior to final decision, unless not feasible, based on safety considerations.

Notes:

- The investigator may decide to evaluate or withdraw the subject from the study based on findings of lesser than grade 3 severity, according to his/her judgment.

3. Consistent Non-compliance with Study Drug (i.e., <80% or >120% compliance at two consecutive study visits; exceptions on a case-by-case basis may be permitted if approved by Sponsor or designee).

Note: Compliance will be evaluated at every study visit during the Treatment Period. If compliance of <80% or >120% is identified at a study visit, the Investigator or designee is to counsel the subject and ensure steps are taken to improve compliance.

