Inpatient Hospitalization/Prolongation of Hospitalization: Any admission (even if less than 24 hours) to a healthcare facility. Admission also includes transfer within the hospital to an acute/intensive care unit (e.g., medical floor to the coronary care unit). Initial and prolonged hospitalizations that **do not** meet this SAE criterion include those due to social and/or convenience reasons (e.g., lack of personal care at home, unable to transfer to non-acute facility), admission to rehabilitation/hospice/skilled nursing facilities, emergency

room visits, same-day/outpatient/ambulatory procedures, and those for pre-planned, elective procedures for a pre-existing condition that did not worsen after the informed consent has been signed (no AE present). However, if the hospitalization was prolonged due to a complication of a pre-existing condition, the complication (diagnosis of same) would qualify as an SAE.

Disability: A substantial disruption of a person's ability to conduct normal life functions.

Life-threatening: Any adverse drug experience that places the patient or subject, in the view of the Investigator, at immediate risk of death from the reaction as it occurred, i.e., it does not include a reaction that had it occurred in a more severe form, might have caused death.

Physical Examination, [REDACTED], Vital Signs, Laboratory Test and ECG Abnormalities: Any abnormalities fulfilling the criteria for an SAE should be reported as such, in addition to being recorded as an AE in the CRF. Any abnormal vital sign, physical [REDACTED] finding or laboratory/ECG result which is clinically significant (i.e., meets one or more of the following conditions) should be recorded as a single diagnosis on the AE page in the CRF:

- Accompanied by clinical symptoms
- Leads to permanent discontinuation of study drug
- Requires a change in concomitant therapy (e.g., addition of, interruption of, discontinuation of, or any other change in a concomitant medication, therapy or treatment).

This does not apply to abnormal vital signs, physical finding or laboratory/ECG results that do not meet the clinical significance criteria or those which are a result of an AE which has already been reported.

Pre-existing conditions that are detected at the Screening Visit (Visit 1), including abnormalities in ECG, physical examination, [REDACTED], vital signs and laboratory tests, are considered to be medical history

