3.6.2 Assessing Adverse Events

When completing appropriate forms for reporting the AE, the Investigator will be asked to assess the AE as follows:

Seriousness of Adverse Event:

- Serious: The AE meets a criterion of the SAE definition.
- Not Serious: The AE does not meet a criterion of the SAE definition.

Severity of Adverse Event:

- Mild: No interference with functioning.
- Moderate: No significant interference with functioning.
- Severe: Significant interference with functioning.

Relationship of Adverse Event (Causality):

The Investigator's causality assessment is the determination whether there is a reasonable possibility that the IMP caused or contributed to the adverse event. Generally, the facts (evidence) or arguments to suggest causal relationship should be documented. Factors to be taken into consideration when assessing causality include: subject's underlying and pre-existing conditions, prior/concomitant medications, timing of onset relative to study drug administration, the known PK characteristics of JTE-051, the currently-known safety profile of JTE-051, known class effects of similar MOA drugs and any other information that is considered relevant by the Investigator.

Akros Pharma Inc. evaluates the relationship of an AE to the study drug using the following three categories:

- Not Related
- Possibly Related
- Related

Action Taken with Regard to Study Drug:

Akros Pharma Inc. evaluates the action taken with the treatment product and/or interacting product using the following four definitions:

- Dose Not Changed: The subject was on treatment with the study drug when the AE occurred, and the study drug dosing was maintained at the same dose level
- Drug Interrupted: The subject was on treatment with the study drug when the AE occurred, and the study drug dosing was temporarily discontinued and then re-started
- Drug Withdrawn: The subject was on treatment with the study drug when the AE occurred, and the study drug dosing was permanently discontinued
- Not Applicable: The subject was not receiving treatment with the study drug when the AE occurred (i.e., AE occurred before the first study drug administration or after the last study drug administration)

Other Action Taken:

- None
- Additional Treatment Given for the AE
- Therapeutic/ Diagnostic Procedure
- Other (including discontinuation/reduction of a concomitant medication due to the AE)

Outcome to Date:

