5. STATISTICAL ANALYSIS

The study was terminated early due to the results of another study on the same compound and slow enrollment in this study. Therefore, the planned sample size of 85 eligible subjects (17 in each treatment group) was not achieved. With only 13 subjects randomized until the early study termination, there will not be enough data to analyze the planned efficacy and safety endpoints. No inferential tests will be performed. Most of the data will be displayed in listings only.

Titles and headers of all statistical analysis tables will indicate the corresponding study population; the number of subjects for the population and for each treatment will be presented in the tables.

Percentages will be presented to 1 decimal, e.g., xx.x%.

Baseline is defined as the last non-missing value prior to the first dose of study drug. Missing data will not be imputed in this study.

Unless otherwise noted, all records collected in the study database, including CRF data and any external data transfers (such as clinical laboratory results) will be displayed in listings, regardless of whether the subject is randomized or not.

All analysis will be performed using SAS® Version 9.4.

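### An asymptomatic laboratory, ECG, vital-sign or physical abnormality for which study drug is interrupted and then restarted is not recorded as an AE, and AE severity takes no account of CTCAE grade

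*Protocol*

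**What the plan says.** Protocol section 3.6.1 gives a general AE definition that allows an abnormal laboratory finding to be an AE. Later in the section, the paragraph on physical examination, vital-sign, laboratory and ECG abnormalities sets a narrower recording rule. An abnormality counts as clinically significant if it meets at least one of three listed conditions:

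- First, the subject has symptoms with the finding.
- Second, the finding ends dosing for good: "Leads to permanent discontinuation of study drug".
- Third, some treatment other than study drug is affected: "Requires a change in concomitant therapy (e.g., addition of, interruption of, discontinuation of, or any other change in a concomitant medication, therapy or treatment".

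The list is introduced as a definition, not as examples, and is followed by an exclusion: "This does not apply to abnormal vital signs, physical finding or laboratory/ECG results that do not meet the clinical significance criteria". The paragraph has one other way in: an abnormality that meets an SAE criterion is recorded both as an SAE and as an AE.

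Section 3.6.2 describes the AE form. One of its action codes covers a case where "the study drug dosing was temporarily discontinued and then re-started". Severity has three levels, all worded as interference with functioning. The lowest is "Mild: No interference with functioning".

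Section 3.4, item 2, uses a different scale. For a subject with CTCAE grade 3 findings, "he/she must be promptly evaluated by the Investigator", with repeat tests, for possible withdrawal.

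On outputs, protocol section 3.8.4.2 commits to by-treatment descriptive tables of laboratory, vital-sign and ECG data, including minimum and maximum. It also plans flags in the listings for potentially clinically significant values, and makes a summary of those values optional. The SAP was written after early termination with 13 subjects randomized. It tabulates TEAEs (section 5.2) and says of the rest: "Most of the data will be displayed in listings only".

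**The concern.** The second condition is limited to permanent discontinuation of study drug. The word interruption appears only in the third condition, where it refers to a concomitant medication. Temporary interruption of study drug is therefore not a reason to record a silent abnormality, although it is a treatment decision that the AE form is built to capture.

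The synopsis names the number, type and severity of AEs as safety assessments. Laboratory and ECG changes are often silent, and the protocol watches for them: the exclusion criteria in section 3.3.2 set cut-offs for blood counts, ALT, AST and creatinine. If such changes are handled by pausing treatment, the TEAE incidence for the affected dose is understated.

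The severity scale raises a related problem. A silent abnormality that is recorded, even one that ends treatment, is graded on functioning alone, while section 3.4 would grade the same finding by CTCAE.

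**Working it through.** The documents give no event rate, so the check is a trace of the rules. Take an on-treatment abnormality that is asymptomatic, has no effect on functioning, is CTCAE grade 3, and does not result from an AE already reported. Apply the three conditions and the SAE route of section 3.6.1, then the severity scale of section 3.6.2.

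| Case | Symptoms | Permanent stop | Concomitant change | SAE criterion | On AE page | Severity levels that fit |
|---|---|---|---|---|---|---|
| A. Drug interrupted and resumed, nothing else | no | no | no | no | **no** | none assigned |
| B. Drug stopped permanently | no | yes | no | no | yes | mild or moderate |
| C. Drug interrupted, concomitant therapy changed | no | no | yes | no | yes | mild or moderate |
| D. Drug interrupted, judged an important medical event | no | no | no | yes | yes (SAE and AE) | mild or moderate |

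*Recording.* Only case A drops out. It is absent from SAP Tables 14.3.1.1 and 14.3.1.2. Its values remain in the SAP data listings (16.2.8.1.1 to 16.2.8.8) and, under the protocol's analysis, in the descriptive tables and flagged listings.

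*Severity.* In cases B to D the top level is unavailable, because it requires significant functional interference. The middle level is worded as no significant interference, which an event with no interference also satisfies, so a site could choose either of the two lower levels.

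*Size, on assumed counts.* At the planned 17 per arm, if 1 to 3 subjects in one arm were case A, the omitted TEAE incidence for that finding would be:

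- 1/17 = 5.9%
- 2/17 = 11.8%
- 3/17 = 17.6%

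The recorded incidence would be 0/17 = 0%. This applies to the full-enrolment design, where the section 3.8.4.2 laboratory tables would also be produced. In the trial as it ended, 13 subjects over five groups is 13/5 = 2.6 per group on average, with every record listed.

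**The case against.** The best defence is that nothing is hidden. At full enrolment the protocol commits to laboratory, vital-sign and ECG tables by treatment with extremes shown. Under the SAP there are 13 subjects, no inferential tests and a listing of every record. This defence largely stands, and it limits the loss to the AE count and grade.

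Several stronger readings are tempting but not supported:

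- *That the safety tables as a whole would miss these findings.* Only the TEAE tables would. The rates worked for 17 per arm cannot be combined with the listings-only SAP, because no version of the trial has both.
- *That a silent grade 3 blood count abnormality is necessarily unrecorded.* Section 3.6.1 names blood dyscrasias without hospitalization as an example of an important medical event, so some would enter by the SAE route. That depends on medical judgment, so the gap is reduced but not closed.
- *That section 3.4 contradicts section 3.6.1.* Section 3.4 says when to evaluate a subject for withdrawal; it is not a recording rule. If the evaluation ends in permanent discontinuation of study drug, 3.6.1 does record the AE.
- *That the interruption code proves interruption was meant to trigger recording.* The code serves every AE, including symptomatic ones.
- *That every silent abnormality is mild by definition.* The middle level also fits the wording. The text supports only that it cannot be severe.
- *That severity tables would mislead.* No table by severity is titled in SAP section 6.1, and the mockups are not in the public text.

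Section 3.5.5 and Tables 4 to 6 are also not in the public text, and the recording paragraph itself contains redactions. A further recording rule there cannot be excluded.

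**Conclusion.** The point holds in a limited form. On the visible text, an asymptomatic abnormality managed by temporary interruption of study drug is left out of the AE record and the TEAE tables, provided that concomitant therapy is unchanged, no SAE criterion is met (including a judged important medical event) and dosing resumes. This sits poorly with the general AE definition and the interruption code, but it is a narrow omission and not an outright contradiction. What is lost is the AE count; the measurements are kept.

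The severity mismatch is separate. A recorded silent abnormality cannot be rated severe, whatever its CTCAE grade. The visible effect is confined to AE records and listings.

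The number of affected subjects is unknown, and the 5.9% to 17.6% range rests on assumed counts at full enrolment. For the 13-subject report the practical effect is small; the weakness is in the protocol rule. Confidence is moderate because of the redactions.

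**What to change.** In section 3.6.1, reword the second condition as *leads to interruption or permanent discontinuation of study drug*. This closes case A and makes the rule fit the action codes in section 3.6.2.

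Then reconcile sections 3.4, 3.6.1 and 3.6.2 on how CTCAE grade 3 findings are recorded and graded. Whether grade 3 alone should trigger recording, and whether the severity scale should change, are open to debate. One modest option is to keep the functional scale and also capture the CTCAE grade for laboratory and ECG AEs, using the version the protocol already cites.

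Both changes concern recording and grading only. They do not affect who is interrupted or withdrawn. The cost is one reworded condition, one grading field or sentence, and a CRF completion note. The downside is a few more AE lines and slightly higher AE rates.

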3.6.2 Assessing Adverse Events

When completing appropriate forms for reporting the AE, the Investigator will be asked to assess the AE as follows:

Seriousness of Adverse Event:

- Serious: The AE meets a criterion of the SAE definition.
- Not Serious: The AE does not meet a criterion of the SAE definition.

Severity of Adverse Event:

- Mild: No interference with functioning.
- Moderate: No significant interference with functioning.
- Severe: Significant interference with functioning.

Relationship of Adverse Event (Causality):

The Investigator's causality assessment is the determination whether there is a reasonable possibility that the IMP caused or contributed to the adverse event. Generally, the facts (evidence) or arguments to suggest causal relationship should be documented. Factors to be taken into consideration when assessing causality include: subject's underlying and pre-existing conditions, prior/concomitant medications, timing of onset relative to study drug administration, the known PK characteristics of JTE-051, the currently-known safety profile of JTE-051, known class effects of similar MOA drugs and any other information that is considered relevant by the Investigator.

Akros Pharma Inc. evaluates the relationship of an AE to the study drug using the following three categories:

- Not Related
- Possibly Related
- Related

Action Taken with Regard to Study Drug:

Akros Pharma Inc. evaluates the action taken with the treatment product and/or interacting product using the following four definitions:

- Dose Not Changed: The subject was on treatment with the study drug when the AE occurred, and the study drug dosing was maintained at the same dose level
- Drug Interrupted: The subject was on treatment with the study drug when the AE occurred, and the study drug dosing was temporarily discontinued and then re-started
- Drug Withdrawn: The subject was on treatment with the study drug when the AE occurred, and the study drug dosing was permanently discontinued
- Not Applicable: The subject was not receiving treatment with the study drug when the AE occurred (i.e., AE occurred before the first study drug administration or after the last study drug administration)

Other Action Taken:

- None
- Additional Treatment Given for the AE
- Therapeutic/ Diagnostic Procedure
- Other (including discontinuation/reduction of a concomitant medication due to the AE)

Outcome to Date:

- Not Recovered/Not Resolved: The subject has not yet recovered from the AE; the event has not improved (follow-up of all serious AEs will be continued until the overall clinical outcome has been ascertained).
- Recovering/Resolving: The subject has not yet recovered from the AE, however, the event is improving (follow-up of all serious AEs will be continued until the overall clinical outcome has been ascertained).
- Recovered/Resolved: The subject recovered from the AE with no sequelae.
- Recovered/Resolved with Sequelae: The subject recovered from the AE with sequelae.
- Fatal: The subject's death was a result of the AE.

3.6.3 Reporting Adverse Events

Adverse Events Reporting

Adverse events occurring (initial occurrence or a worsening of a pre-existing condition) after the informed consent has been signed and up to 4 weeks (28 days) after the last dose of study drug will be reported and included in the study database. However, pre-existing conditions detected as part of the screening procedures should be documented as medical history. Worsening of the underlying condition (i.e., plaque psoriasis) or signs/symptoms associated with this condition should not be reported as an AE unless they meet at least one serious criterion; in such case when they would be reported as both an AE and an SAE. Adverse events will be reported on the AE CRF page.

Serious Adverse Event Reporting

Reporting by Investigators

Detailed instruction regarding SAE reporting will be provided in the appropriate documents outside of this protocol. A brief, non-all-inclusive summary is provided below.

Any SAE experienced by a study subject after signing the informed consent up to 28 days after the last dose of study drug will be reported to the Sponsor or designee. Additionally, SAEs that occur after this period will also be reported to the Sponsor or designee if the Investigator considers the SAE possibly related or related to the study drug.

Serious adverse events (both initial reports and follow-up information) must be reported to the Sponsor or designee within 24 hours of the Investigator's (site's) awareness or notification of the event.

The Investigators should make every effort to provide complete information when reporting the SAE (both for initial reports, as well as for follow-ups).

The Investigator must continue to follow the subject until the SAE has subsided, the condition becomes chronic in nature, stabilizes (in the case of persistent impairment), or the subject dies. Within 24 hours of receipt of follow-up information, the Investigator must submit it to the Sponsor or designee.

The Investigator is also required to submit SAE reports to the IRB/IEC in accordance with local requirements. All investigators involved in studies using the same IMP will receive any Suspected Unexpected Serious Adverse Reaction (SUSAR) reports for onward submission to their local IRB/IEC as required. All reports sent to investigators will be blinded.

Reporting by the Sponsor

Competent authorities and IRBs/IECs will be informed by the Sponsor or designee of SUSARs according to the local requirements. Additionally, all SUSARs will be reported by the Sponsor or designee into the EudraVigilance system, as appropriate. Cases will be unblinded by designated personnel for reporting purposes as required.

Exposure *in Utero* Reporting:

If a female subject becomes pregnant or the female partner of a male subject participating in the study becomes pregnant after the subject receives the first dose of study drug, or within

28 days of discontinuing study drug, the Investigator should report the pregnancy to the Sponsor or designee within 24 hours of being notified.

The subject/partner should be followed by the Investigator until completion of the pregnancy. If the pregnancy ends for any reason before the anticipated date, the Investigator should notify the Sponsor or designee. At the completion of the pregnancy, the Investigator will document the outcome of the pregnancy. If the outcome of the pregnancy meets the criteria for immediate classification as an SAE (i.e., spontaneous abortion, stillbirth, neonatal death, or congenital anomaly), the Investigator should follow the procedures for reporting an SAE as described above.

Overdose Reporting:

An overdose is a significant variation from the recommended/scheduled dosage for a product. For the purposes of this study, overdose is defined by any confirmed use of blinded study medication of more than four tablets once a day. If such situations occur, the Investigator should provide additional training to the subject on study drug dosing instructions and emphasize the importance of compliance. Currently there is no known antidote to JTE-051, thus appropriate symptomatic and/or supportive care is to be provided at the Investigator's discretion, as needed. The subject's continued eligibility will be left to the judgment of the Investigator.

Information on overdoses in subjects is collected by the Sponsor or designee. Should a subject experience an overdose during the course of the study, the investigator or qualified designee must report the overdose as soon as possible, but not later than the timeframe requested by the Sponsor or designee after the investigator or qualified designee first becomes aware of the overdose. Instructions will be provided on how to collect this information.

[figure not shown]

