3.3.1 Inclusion Criteria

To qualify for the study, the subject must satisfy the following criteria:

1. Male or female, ≥ 18 and ≤ 70 years of age at the time of Visit 1 (Screening Visit);
2. Have had a diagnosis of moderate to severe plaque psoriasis for at least 6 months prior to Visit 1;
3. Plaque-type psoriasis covering $\geq 10\%$ of Body Surface Area (BSA) at Visit 1 and Visit 2 (Baseline);
4. Psoriasis Area and Severity Index (PASI) score ≥ 12 at Visit 1 and Visit 2;
5. Static Physician's Global Assessment (sPGA) score ≥ 3 at Visit 1 and Visit 2;

-
6. Body Mass Index (BMI) ≤ 40 kg/m² at Visit 1;
 7. Females may participate if they meet one of the following criteria:
 - Surgically sterile (e.g., hysterectomy or bilateral oophorectomy),
 - At Visit 1, females with a documented history of lack of menses for ≥ 12 consecutive months with no other reversible medical etiology will be considered postmenopausal.
 - At Visit 1, if positive for lack of menses but onset < 12 months, then an FSH > 40 will be required to define post-menopausal status, otherwise subject is considered of childbearing potential, or
 - If of childbearing potential, with a negative pregnancy test at Visit 1 and if participates in heterosexual intercourse, agrees to be compliant with the consistent and correct use of acceptable methods of contraception as described below. Acceptable methods of birth control for this study are:
 - a) one highly effective contraceptive method of birth control, which includes intrauterine devices, partner sterilization (with the appropriate post-vasectomy documentation of the absence of sperm in the ejaculate), tubal ligation, bilateral tubal occlusion, intrauterine hormone-releasing systems, **in addition to**
 - b) one effective method of birth control, which includes male condom, female condom, cervical cap, diaphragm or contraceptive sponge all with spermicide (hormonal methods are not allowed).The above described contraception methods must be maintained for the duration of the study and for at least 30 days after the last dose of study drug.
 8. Male subjects must agree to use a barrier contraceptive method with spermicide for the duration of the study and for at least 12 weeks after the last dose of study drug or be sterilized (with appropriate post-vasectomy documentation of the absence of sperm in the ejaculate):

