Male subjects should be informed about the risks involved if pregnancy in female partners occurs while he is taking an investigative product and for at least 12 weeks after the last dose of study drug. Counseling on the appropriate contraception methods for their female partners should be given as follows: female partners of male subjects randomized in this study must be post-menopausal or in case of female partner of childbearing potential, unless surgically sterile, they must agree to use at least one form of an acceptable form of birth control (in addition to the method utilized by the male subject) for the duration of the study and for at least 12 weeks after the last dose of study drug. Please see inclusion criterion # 7 for a list of acceptable forms of birth control for the study (hormonal methods will be allowed for females partners of male subjects);

Additionally, male subjects must not donate sperm for the duration of the study and within 12 weeks of the last dose of study drug.
 9. [REDACTED]
 10. Able and willing to complete an [REDACTED] questionnaire responses on a mobile device on a daily basis for the duration of the study;
 11. Able and willing to give written informed consent.

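### Mandatory pregnancy reporting stops 28 days after study drug is stopped, while the eligibility criteria use a 12-week post-dose horizon for partner pregnancy and for planned pregnancy in female subjects

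*Protocol*

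**What the plan says.** **Reporting rule.** Protocol Section 3.6.3, Exposure in Utero Reporting, applies to female subjects and to partners of male subjects. Its partner clause reads "female partner of a male subject participating in the study becomes pregnant after the subject receives the first dose of study drug, or within"; the time limit and the duty attached to it are "28 days of discontinuing study drug, the Investigator should report the pregnancy to the Sponsor or designee within 24 hours of being notified". A reported pregnancy is then followed by the investigator until it ends, and its outcome is documented.

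**Male subjects.** Inclusion criterion 8 (Section 3.3.1) uses a 12-week post-dose period throughout:
- Contraception: the subject "must agree to use a barrier contraceptive method with spermicide for the duration of the study and for at least 12 weeks after" dosing ends, unless sterilized. A partner of childbearing potential, unless surgically sterile, also uses a method for at least 12 weeks.
- Counselling: the protocol wants him "informed about the risks involved if pregnancy in female partners occurs while he is taking an investigative product and for at least 12 weeks" once dosing has ended.
- Sperm donation: "male subjects must not donate sperm for the duration of the study and within 12 weeks of the last dose of study drug".

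**Female subjects.** Under inclusion criterion 7, contraception "must be maintained for the duration of the study and for at least 30 days after the last dose of study drug". Exclusion criterion 29 (Section 3.3.2) also excludes women who plan to become pregnant during the study or in the 12 weeks after the last dose.

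**Neighbouring safety rules.** The SAE duty in Section 3.6.3 covers "Any SAE experienced by a study subject after signing the informed consent up to 28 days after the last dose of study drug". Later SAEs are reportable if the investigator considers them possibly related or related. The protocol says of its own SAE text: "A brief, non-all-inclusive summary is provided below".

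**The concern.** The protocol warns male subjects about partner pregnancy for at least 12 weeks after dosing, yet stops asking for reports of such pregnancies after 28 days. A partner pregnancy starting in week 6 after the last dose lies inside the warned period. Nothing in the visible text obliges anyone to report it or to follow it to outcome. For female subjects, a pregnancy starting then falls inside the horizon of exclusion criterion 29 and is likewise outside the reporting rule.

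Detection in that interval is also weak. Female subjects of childbearing potential have urine tests through Visit 7 (Section 3.5.6.22), but partners are not tested. Visit 7 is the last scheduled contact, so a later pregnancy becomes known only if the subject tells the site.

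What is at stake is the completeness of the safety record on pregnancy exposure. Efficacy is not involved.

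**Working it through.** The plan gives no figure to reproduce. The check compares the stated windows and then sizes the gap.

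**1. Windows after the last dose**

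| Rule | Post-dose period |
|---|---|
| Pregnancy reporting, Section 3.6.3 | 28 days |
| Criterion 8: male and partner contraception, counselling, sperm donation | 12 × 7 = 84 days (a minimum for all but sperm donation) |
| Criterion 7, female contraception | at least 30 days |
| Criterion 29, no planned pregnancy | 12 × 7 = 84 days |

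**2. Gap**
- Partners, against criterion 8: 84 − 28 = 56 days (days 29 to 84).
- Female subjects, against criterion 7: 30 − 28 = 2 days.
- Female subjects, against criterion 29: 84 − 28 = 56 days.

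**3. Gap as a share of the period**
- Of the post-dose part: 56/84 = 67%.
- Of the whole partner-risk period: criterion 8 also counts time on drug. The last dose is the day before Visit 6 (Day 84 ± 2), so there are about 83 treatment days, all inside the reporting rule. 56/(83 + 84) = 56/167 = 34%.

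**4. Last scheduled contact.** Visit 7 is Day 112 ± 2 and the last dose is about Day 83 (81 to 85). The interval is 112 − 83 = 29 days, with extremes 110 − 85 = 25 and 114 − 81 = 33. Nearly all of the gap lies after the last visit.

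**5. Expected partner pregnancies in the gap.** These inputs are assumptions, not from the documents: 50–70% of JTE-051 subjects are male, 30–60% of those have a partner of childbearing potential, and 1–5 pregnancies occur per 100 partner-years on contraception.
- Planned size: 4 × 17 = 68 on JTE-051. Males with such a partner: 68 × 0.5 × 0.3 = 10.2 to 68 × 0.7 × 0.6 = 28.6. Times 56/365 gives 1.56 to 4.38 partner-years. Times 0.01 and 0.05 gives **0.016 to 0.22**.
- As enrolled: SAP Section 5 reports 13 randomized. With equal allocation, 13 × 4/5 = 10.4 on JTE-051. The same steps give 1.56 to 4.37 males with such a partner, 0.24 to 0.67 partner-years, and **0.002 to 0.034** pregnancies.

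**6. Female subjects.** The same rate cannot be carried over, because their contraception duty may end at 30 days. A break-even is more useful. If half of the 68 are women and all could conceive, exposure in the gap is 34 × 56/365 = 5.2 woman-years. One expected pregnancy would need 1/5.2, or about 19 per 100 woman-years, in a group selected for not planning pregnancy. As enrolled, 5.2 women × 56/365 gives only 0.80 woman-years.

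**The case against.** **The 28 days are coherent with the rest of the plan.** They match the AE and SAE windows and the 4-week Follow-up Period, which Protocol Section 1.3.2 calls conservative on pharmacokinetic grounds (that sentence is cut off in the public text). A precautionary contraception period need not equal a mandatory reporting window. This stands as a reason for low severity. It does not remove the mismatch: the AE and SAE windows concern events in the subject, whereas the 12 weeks were chosen specifically for conception.

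**Other rules may catch the case.** Congenital anomaly is an SAE criterion, and late related SAEs are reportable. But the SAE duty is written for study subjects, which a partner is not, and a pregnancy is not itself an SAE. Section 3.6.3 sends only certain outcomes to SAE reporting, and the outcome is sought only for pregnancies already being followed. The fallback is arguable at best. SAE instructions outside the protocol may say more and cannot be checked here.

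**The rule might be read as open-ended after the first dose.** The 28-day clause would then do nothing, so a cut-off is the natural reading.

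**Stronger readings the documents do not support.** A reader might infer that two thirds of the partner-risk period is uncovered. That share applies only after the last dose; over the whole period it is about one third. A reader might also infer that conception on days 29 to 84 is known to be hazardous. The nonclinical and clinical sections are not in the public text and the basis for 12 weeks is not visible, so the documents show an inconsistency between windows, not a residual risk.

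**Conclusion.** The inconsistency is real, narrow and of low severity. For 56 days after the reporting limit, the visible protocol states no duty to report a partner pregnancy or follow it to outcome, although its own criterion 8 treats that time as part of the warned period. For female subjects the shortfall is 2 days against the contraception period and 56 days against the no-planned-pregnancy horizon. Criterion 29 concerns intention at entry and is not a statement of exposure risk, so the case is firmer for partners.

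Fewer than one partner pregnancy is expected in the gap at either sample size. That rests on the assumed sex mix, partner share and pregnancy rate; for women it rests on the break-even above. No endpoint or analysis changes. The trial stopped early, so if follow-up is already complete the practical value lies mainly in later protocols that reuse this wording. It is worth considering because it is cheap, not because harm has been shown.

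**What to change.** In Section 3.6.3, Exposure in Utero Reporting, replace the 28-day limit with one limit for female subjects and for female partners of male subjects: *from the first dose of study drug until 12 weeks after the last dose*. A single limit matches criteria 8 and 29, covers the minimum in criterion 7, gives a definite end date, and avoids a shorter window for directly exposed women than for partners. Keep the 24-hour reporting time and the outcome follow-up as they are.

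Add to Visit 7 a reminder that subjects should tell the site about any pregnancy, their own or a partner's, that starts in that period.

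**Cost.** One reworded sentence and one spoken reminder at an existing visit, made by amendment under Section 5.2. There is no extra visit, test, call or contraception duty. The real burden is that sites must accept reports for 56 more days and follow each added pregnancy to completion after the subject's last visit, in some cases in a partner who was never a trial subject. Late reports will still depend on subjects coming forward.
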